### **Hypothesis:**

BDV is an indicator of infection and provides the earliest possible means for detection of infections.

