### 3.0 Study design and rationale

This is a multi-center prospective study to assess exhaled  $^{13}\text{CO}_2/^{12}\text{CO}_2$  BDV as an indicator of infection in critically ill adult ICU subjects. Critically ill adult ICU subjects who are not suspected of having an infection at the time of ICU admission will be enrolled as study subjects. Up to 100 Subjects will be enrolled from 8-10 centers across the United States.

This study is needed to determine the rate of infection detection of the Canary device. Logistic considerations include the definition of an infection and collection of data needed to diagnose infections consistent with the Centers for Disease Control (CDC) standards (16), and determination of onset timing of infection by clinical standards and by BDV. The BDV, as determined by the Canary™, will be retrospectively determined from exhaled breath samples, and will not be available or used clinically to establish or confirm the infection.

Effectiveness parameters will be estimated to determine the sample size required for the subsequent pivotal study. Parameters to be estimated include: timing of the infection onset, the lead time offered by various BDV thresholds, sensitivity of the BDV threshold, specificity of not reaching the BDV threshold, the receiver operating curve as a function of the BDV threshold, and the positive and negative predictive values based on hypothetical infection incidence. Models for infection outcome (Y/N) will be analyzed for the impact of clinical and on study covariates. The corresponding performance of a conventional best practices control (BPC) will be compared to determine if the Canary can identify infections earlier in the clinical course than BPC. Several time windows will be tested to determine the timing of and criteria for aligning a monitoring test result with BPC or clinical reference standard result. This pilot study will be used to formulate strategies to help control the Type I error (“false positive”) associated with multiple times when BDV could become positive. The pilot study will assess the robustness of the effectiveness outcomes across a broad spectrum of possible infection types.

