## 5. Analysis Objectives

The overall objective of the analysis is to demonstrate that the BDV is a leading marker for infection diagnosis in critically ill subjects. Key questions to be answered are 1) Evaluate the BDV as a marker of infections in critically ill subjects at risk of progressing to severe sepsis and septic shock; 2) To measure variation of BDV with time in critically ill ICU patients progressing to severe sepsis and septic shock among those who agree to participate as research subjects; 3) To determine the magnitude of change of BDV in subjects who subsequently progress to severe sepsis and septic shock; 4) To define variation of BDV in critically ill ICU subjects who do not progress to severe sepsis and septic shock.

The BDV will be analyzed to determine the range of exhaled  $^{13}\text{CO}_2/^{12}\text{CO}_2$  BDV in adult subjects. The  $^{13}\text{CO}_2/^{12}\text{CO}_2$  BDV will be compared with current clinical standard scores, physiologic measurements and biomarkers (e.g. vital signs, WBC, CRP, PCT), and any interventions -- such as antibiotic administration -- will be noted for the purpose of assisting in understanding variation of BDV. For the purpose of defining a positive BDV for the presence of an infection, a positive BDV is defined as a change of greater than 1‰ within a 24-hour period above or below the baseline value. The 1‰ threshold for change in the BDV within 24 hours is based on the variability of approximately 0.5‰ seen in subjects with stable nutrition who do not develop infections. Thus, a change of 2 standard deviations away from the pre-infection mean will be examined as part of sensitivity among those with progression to severe sepsis and septic shock and positive predictive value for progression to severe sepsis and septic shock.

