## **6. Analysis Sets/Populations/Subgroups**

The first task is to demonstrate that there is a positive signal associated with the Canary test using the subject as their own control.

A per protocol analysis will be performed following EAC event reconciliation and subsequent database lock. The EAC will determine diagnostic truth by documenting severe sepsis or septic shock events as well as the onset and resolution dates.

Infection documentation will be reviewed by the EAC committee based on best clinical practices, using four categories:

- No suspicion of infection
- Inconclusive evidence of infection
- High suspicion of infection
- Overt infection

For sensitivity and specificity, non-inferiority testing will be performed to rule out a -10% disadvantage according to a one-sided 97.5% lower confidence limit for the BDV – PCT

difference; exact McNemar paired comparison tests will be performed to test BDV non-inferiority relative to PCT. Both endpoints must achieve statistical significance in order to achieve study success.

PPV and NPV will be computed as observed and for a range of possible infection prevalence (10%, 20%, 30%, and 40%). Results will be analyzed in the same manner as sensitivity and specificity.

BDV variations will be assessed using a two-sample t-test to compare the averaged (across time points) BDV between subjects who are diagnosed with a severe sepsis and sepsis shock vs. no severe sepsis or sepsis shock. Also a linear mixed effects model with subject specific random effects will be used to compare BDV measurements between the two diagnostic groups. This model will be also used to estimate the intra- and inter-subject variability of the BDV measurements. A paired t-test will be used to compare the BDV measurements prior to and after a diagnosis of infection or sepsis.

The definition of a positive BDV will be based on a 72-hour window without advance knowledge of the diagnosis. In the absence of clinical details supporting PCT operating characteristics (sensitivity, specificity), two PCT thresholds (0.5 and 2.0) will be evaluated but the 0.5 threshold is deemed to be primary for BDV comparison.

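### The SAP sets out to show that BDV is a leading marker, but its success rule tests only accuracy against PCT and no analysis in the SAP estimates lead time

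*SAP*

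**What the plan says.** **Aim.** SAP section 5 states: "The overall objective of the analysis is to demonstrate that the BDV is a leading marker for infection diagnosis in critically ill subjects". The hypothesis in the Protocol's Study Summary is "BDV is an indicator of infection and provides the earliest possible means for detection of infections". Protocol 3.0 lists the lead time at various BDV thresholds among the parameters to estimate, and says the performance of a best practices control (BPC) will be "compared to determine if the Canary can identify infections earlier in the clinical course than BPC".

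**Success rule.** In SAP section 6, "non-inferiority testing will be performed to rule out a -10% disadvantage according to a one-sided 97.5% lower confidence limit", and "exact McNemar paired comparison tests will be performed to test BDV non-inferiority relative to PCT". This applies to sensitivity and to specificity, and "Both endpoints must achieve statistical significance in order to achieve study success". The only secondary hypothesis, in SAP section 5, concerns BDV variability after diagnosis.

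**Where time enters.** SAP section 6 says: "The definition of a positive BDV will be based on a 72-hour window without advance knowledge of the diagnosis". It does not say what anchors that window. For PCT it says "two PCT thresholds (0.5 and 2.0) will be evaluated but the 0.5 threshold is deemed to be primary for BDV comparison" and gives no window. Protocol 3.0 compares a sustained BDV fall with a diagnosis in the next 72 hours. Protocol 7.2 and SAP section 9 carry this out with Fisher's exact test and kappa. The EAC documents onset as a date.

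**The concern.** Earlier detection is the reason given for the device. The success rule takes three inputs: BDV positive or negative, PCT positive or negative, and EAC truth. The order of the two tests, and the interval from either one to diagnosis, do not enter it. Followed exactly, the plan can report success under an objective about leading without having estimated any lead. A reader of the report could then take non-inferior accuracy as evidence of earlier detection.

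**Working it through.** **1. The SAP's own power figures.** Inputs from SAP section 6, Tables 1 and 2: n = 97 pairs, margin 0.10, one-sided 2.5%. The power column has difference d = 0.10 and discordance η = 0.40. The N-I column has d = 0.015 and η = 0.315.

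Power = Φ[(d + 0.10)/√((η − d²)/n) − 1.96]

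- Power column: √((0.40 − 0.01)/97) = 0.0634; 0.20/0.0634 − 1.96 = 1.19; power 88%. The SAP states 89% and 87%.
- N-I column: √((0.315 − 0.0002)/97) = 0.0570; 0.115/0.0570 − 1.96 = 0.06; power 52%. The SAP states 51% and 52%.

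The stated figures reproduce within the noise of 1000 simulations (standard error about 1 point).

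**2. Probability of meeting the rule.** Events and non-events are separate sets, so the two powers are multiplied.

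- Planning values: 0.89 × 0.87 = 77% (exact enumeration of a Wald limit also gives about 78%; with a continuity correction, 72%).
- N-I column: 0.51 × 0.52 = 27%.
- Equal accuracy, with an assumed discordance of 0.30 to 0.40: about 12% to 20%.

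No time appears in the formula. A delay of BDV behind PCT leaves each figure unchanged as long as every BDV positive still counts as positive.

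**3. What the window could change.** Suppose lateness pushes a share f of the both-positive events (60% in Table 1) outside the 72-hour window, and these count as BDV misses. This is an assumption, because the anchor is not stated. Then d = 0.10 − 0.60f and η = 0.40 + 0.60f for sensitivity.

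| f | d | η | Sensitivity power | Joint |
|---|---|---|---|---|
| 5% | 0.07 | 0.43 | 73% | 64% |
| 10% | 0.04 | 0.46 | 53% | 47% |
| 20% | −0.02 | 0.52 | 19% | 17% |

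The window can therefore penalise a very late BDV, but it still does not compare BDV with anything in time.

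**4. Does another analysis supply the lead?** Protocol 7.2 and SAP sections 6 and 9 contain t-tests, a mixed model, Fisher and kappa, and accuracy measures. Only Fisher and kappa look forward in time. They score a lead of 1 hour the same as one of 71 hours, and they are outside the success rule.

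**5. What a lead-time analysis could deliver.** BDV is positive in 0.85 × 97 ≈ 82 events, and both tests are positive in 0.60 × 97 ≈ 58. As a rough guide to the 95% half-width for a mean in 58 events, 1.96 × SD/√58 gives 6.2, 9.3 and 12.4 h for an assumed SD of 24, 36 and 48 h.

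**6. A trap in comparing with PCT.** BDV is sampled every 4 h and PCT once a day. If positivity arises at random between samples, the mean detection delays are 2 h and 12 h, which is an artificial lead of 10 h. Setting never-positive tests to onset time adds to it, because 25% of events are BDV-only and 15% PCT-only. Simulations of a signed-rank test built this way, with zero true lead (97 events, Table 1 proportions, assumed positivity centred 30 to 60 h before onset, assumed SD of the difference 0.5 to 36 h), concluded a lead in roughly three quarters to all of the runs. With BDV read only at PCT draw times, in both-positive events, the rate was about 3% or less.

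**The case against.** The strongest reply is that non-inferior accuracy is a legitimate success criterion, that the SAP claims only comparable performance against PCT, and that the rule tests exactly that. The objective speaks of leading diagnosis and Protocol 3.0 of best practice. Neither promises a lead over PCT, so a BDV that trails PCT but precedes diagnosis would still meet the aim. Nor are the documents silent on timing: Protocol 3.0 says how the leading-indicator hypothesis is to be assessed, and that analysis is planned.

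All of this stands, and it rules out three stronger readings that a reader might infer.

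- *That a BDV later than PCT in every event would succeed 77% of the time.* In the 40% of events that are discordant in Table 1, only one test turns positive, so later has no meaning there.
- *That 77% is an error rate.* It is the planned joint power when BDV is 10 points better on both measures.
- *That lateness can never matter.* Step 3 shows that it might, depending on the anchor.

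The reply does not close the gap. The success rule tests lead against neither diagnosis, best practice nor PCT, and the lead time listed in Protocol 3.0 has no matching analysis in Protocol 7.2 or the SAP.

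**Conclusion.** The point holds in this form: meeting both co-primaries cannot support a conclusion that BDV is leading or earlier, because the rule does not use timing and no planned analysis estimates lead time. At the SAP's planning values success has a probability of about 77%, and trailing PCT within the window would not reduce it. That figure assumes a 10-point BDV advantage on both measures, 97 pairs each, independent event and non-event sets, and late positives that still count. It is about 27% at the N-I column values. The accuracy comparison itself is not undermined. What is missing is the link from it to the stated objective.

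**What to change.** 1. **Limit the claim.** State in SAP section 6 that meeting both co-primaries supports only accuracy non-inferior to PCT, and that leading or earlier will be concluded only from a lead-time analysis. State the anchor of the 72-hour window and give PCT a window.
2. **Add a key secondary, tested only after both co-primaries succeed.** Analyse the time from first positive BDV to EAC onset or clinical diagnosis, with a 95% CI for the median. Let the window extend past onset so that the lead is not positive by construction. Show the same quantity at matched times in non-event subjects, because chance alarms alone can look like a lead. Make the same comparison with first SIRS/MEWS positivity in the window as best practice. The SAP would have to define that control, including a MEWS cut-off, which Protocol 6.1 does not give.
3. **If a lead over PCT is also to be claimed,** make the primary comparison BDV read only at PCT draw times, in events positive on both tests, and report discordant events separately. Do not set negatives to onset time, and do not use 4-hourly BDV against daily PCT as the main test.
4. **Record onset time.** Have the EAC record onset to the hour where the record allows.

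**Cost.** SAP wording, one added analysis and some EAC effort. Breath and blood collection times are already recorded. Gating leaves the co-primary alpha untouched. The leading claim becomes harder to win, and a PCT comparison would rest on about 58 of 97 events, which limits its precision.

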For critically ill patients admitted to an ICU, the mean overall nosocomial infection rate is 6 to 18% (29, 30, 40). The incidence rate of infection could be greater for all surgical ICU patients. The infection rate in the previous proof-of-concept study was 50% using the same population and inclusion/exclusion criteria; this assumption of equal proportions of prospectively enrolled infected and uninfected subjects will be used in the sample size calculations which follow. Data collected to date indicate that a sustained change in BDV of 1.0‰ or more correlates with the presence of infection when the subject is used as his-her control. The average intra subject standard deviation (SD) across time points in critically ill adult subjects previously studied was 0.95‰, regardless of the underlying medical conditions. The inter subject SD is expected to be 1.0‰ at most. Using the BDV measurements during the breath sample monitoring period (breath sample assessments every 4 hours), the expected overall SD of the mean BDV measurements (across time points) is less than 1.0‰.

BDV sensitivity and specificity will be evaluated relative to PCT sensitivity and specificity according to non-inferiority hypothesis tests where a greater than 10% BDV disadvantage is to be ruled for both sensitivity and specificity relative to a less than 10% BDV disadvantage. The BDV sensitivity and specificity estimates will then be used to determine the positive predictive value (PPV) and negative predictive value (NPV) once the prevalence is known; prevalence surrogates can be used to apply the observed sensitivity and specificity to various ICU and CCU settings.

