### Objectives

To determine the following:

1. Evaluate the BDV as a marker of infections in critically ill subjects at risk of progressing to severe sepsis and septic shock;
2. To measure variation of BDV with time in critically ill ICU patients at risk of progressing to severe sepsis and septic shock among those who agree to participate as research subjects;
3. To determine the magnitude of change of BDV in subjects who subsequently progress to severe sepsis and septic shock;
4. To define variation of BDV in critically ill ICU subjects who do not progress to severe sepsis and septic shock.
5. Compare sensitivity and specificity, and positive and negative predictive value of the PCT marker with the BDV.

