Descriptive statistics will be generated for patient characteristics, demographics, and on-study events relating to subgroups (see Section 7.4). For continuous variables, descriptive statistics may include the number of subjects from whom data was used in the calculation, mean, standard deviation, median, minimum, and maximum; frequencies and percentages may be displayed for categorical data.

The predicate marker PCT sensitivity is estimated to be between 64-82% based on a recent review of the published literature (19); PCT sensitivity will be assumed to be 75% for sample size calculations. BDV sensitivity is expected to range between 80-90% based on the proof-of-concept study. The study is designed to have at least 80% power and one-sided 2.5% Type I error. A greater than 10% disadvantage for BDV vs PCT (null hypothesis) is to be tested against a less than 10% disadvantage for BDV vs PCT (alternative hypothesis). As shown in Table 1, this non-inferiority hypothesis can be tested with 97 documented infection events. The BDV advantage vs PCT resulting in a -10% one-sided 97.5% lower confidence bound (CB) is also displayed in Table 1; if the sensitivities are 76.5% for BDV vs 75% for PCT based on 97 pairs of infection events, then the one-sided 97.5% lower CB would be -10%, which would establish BDV non-inferiority relative to PCT.

Table 1: One-sided 97.5% Lower 97.5% Confidence Limit: Sensitivity Paired Differences (simulation)

	Power	N-I
Confidence level, 1-<math>\alpha</math> (one-sided)	0.975	0.975
Expected difference, <math>\pi_T - \pi_S, \Delta_1</math>	0.100	0.015
Proportion discordant, <math>\eta = \pi_{10} + \pi_{01}</math>	0.400	0.315
Proportion both yes, <math>\pi_{11}</math>	0.600	0.600
Lower limit for <math>\pi_T - \pi_S, LL</math>	-0.100	-0.100
Number of simulations	1000	1000
Random seed for simulations	123	123

Power (%)	89	51
n (number of pairs)	97	97

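### The SAP carries the paired non-inferiority method for sensitivity and specificity over to PPV and NPV, where exact McNemar is not defined and the -10 point margin has no stated basis

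*SAP*

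**What the plan says.** For sensitivity and specificity, SAP section 6 (Analysis Sets/Populations/Subgroups) says that "non-inferiority testing will be performed to rule out a -10% disadvantage according to a one-sided 97.5% lower confidence limit" for the BDV minus PCT difference, and that "exact McNemar paired comparison tests will be performed to test BDV non-inferiority relative to PCT". Both endpoints must succeed for the study to succeed.

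The next paragraph has PPV and NPV computed as observed and at four prevalences from 10% to 40%, and then says "Results will be analyzed in the same manner as sensitivity and specificity".

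Four other places bear on this:

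- SAP section 5, Objectives, makes the comparison objective 5: "Compare sensitivity and specificity, and positive and negative predictive value of the PCT marker with the BDV".
- SAP section 5 says that predictive values will be worked out from the sensitivity and specificity estimates once a prevalence is supplied.
- The text before Table 2 in section 6 defends the 10% delta, but for sensitivity and specificity only.
- SAP section 9 adds 95% confidence intervals for all four measures. It names no method for the BDV minus PCT difference.

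**The concern.** Sensitivity and specificity condition on true status. Every infected subject has both a BDV and a PCT result, so each is a pair, and the same holds for every non-infected subject. PPV and NPV condition on each test's own result, so the two tests have different denominators. A method built on discordant pairs within one common denominator does not transfer.

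The margin is a separate matter. Ten points of sensitivity is not equivalent to ten points of PPV or NPV, whose possible range depends on prevalence.

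At stake is the predictive-value part of objective 5. As written, the programmer would have to choose a method after database lock. A non-inferiority statement on NPV at low prevalence could also be made for a test that carries no information.

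**Working it through.** **Inputs (SAP section 6 and Tables 1 and 2).** There are 97 infected and 97 non-infected pairs. "PCT sensitivity will be assumed to be 75% for sample size calculations", with a range of 64 to 82%. PCT specificity is assumed to be 65%, with a range of 56 to 78%. In the power columns the expected difference is 0.10 and the discordant proportion 0.40, with both-yes proportions of 0.60 and 0.10.

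**1. The plan's own figures.** Power = Φ((Δ + 0.10)/√((η − Δ²)/n) − 1.96).

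- Δ = 0.10, η = 0.40: 0.20/√(0.39/97) − 1.96 = 1.19, giving 88.4% (stated 89% and 87%).
- Δ = 0.015, η = 0.315: 0.115/√(0.314775/97) − 1.96 = 0.06, giving 52.3% (stated 51% and 52%).

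The tables reproduce within 2 points. They concern sensitivity and specificity; the SAP gives no figure for PPV or NPV.

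**2. Denominators.** The infected cells are: both positive 0.60, BDV only 0.25, PCT only 0.15, neither 0. That is sensitivity 85% and 75%. For the non-infected I read the 0.10 in Table 2 as both falsely positive. This is the only reading consistent with specificities of 75% and 65% and 0.40 discordance, because both correctly negative is then (0.75 + 0.65 − 0.40)/2 = 0.50 and the remainder is 0.10.

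- BDV-positive: 97 × (0.85 + 0.25) = 106.7.
- PCT-positive: 97 × (0.75 + 0.35) = 106.7.
- Positive on both: 97 × (0.60 + 0.10) = 67.9. So 38.8 are positive on BDV only and 38.8 on PCT only.
- Negative: 87.3 for each test, of whom 97 × 0.50 = 48.5 are negative on both.

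The PPVs are 82.45/106.7 = 77.3% for BDV and 72.75/106.7 = 68.2% for PCT. If one forced a common denominator by keeping only the 67.9 positive on both, each test would have PPV 58.2/67.9 = 85.7%. A subject's true status is the same whichever test is considered, so there are no discordant pairs and the difference is 0 by construction.

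**3. Fixed prevalences.** With prevalence p, PPV = Se·p/(Se·p + (1 − Sp)(1 − p)) and NPV = Sp(1 − p)/(Sp(1 − p) + (1 − Se)p). These are functions of estimates. There is no table of paired counts on which to run an exact test.

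**4. The margin against an uninformative test** (PPV = p, NPV = 1 − p), PCT at 75%/65%:

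| Prevalence | PCT PPV | Deficit, points | PCT NPV | Deficit, points |
|---|---|---|---|---|
| 10% | 19.2% | 9.2 | 95.9% | 5.9 |
| 20% | 34.9% | 14.9 | 91.2% | 11.2 |
| 30% | 47.9% | 17.9 | 85.8% | 15.8 |
| 40% | 58.8% | 18.8 | 79.6% | 19.6 |

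At 10% both deficits lie inside the margin; at 20 to 40% both lie outside it.

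Over the corners of the SAP's PCT range at 10% prevalence, the NPV deficit runs from 3.3 points (64%/56%) to 7.5 (82%/78%), always inside. The PPV deficit runs from 3.9 (64%/56%) to 19.3 (82%/78%), so for PPV the answer depends on PCT's performance. The 20 to 40% result also depends on it: at 64%/56% the PPV and NPV deficits are 6.7 and 6.2 points at 20% prevalence, inside the margin.

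**5. Chance of passing at 10% prevalence.** I used 97 + 97 pairs, a delta-method 97.5% lower limit, 20,000 simulations, PCT at 75%/65%, and BDV and PCT assumed conditionally independent.

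- A coin-flip test (50%/50%) is declared non-inferior on NPV about 74% of the time and on PPV about 6%.
- A BDV exactly at both co-primary margins (65%/55%) passes NPV over 99% of the time and PPV about 39%.

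**The case against.** **The SAP never writes McNemar or -10% for PPV and NPV.** This is true. No predictive-value hypothesis is listed, the delta is defended only for the co-primaries, and section 9 could support an interval-only reading. A confidence limit for the difference in predictive values is also well defined. But the phrase points to a paragraph made up of a margin, a limit and a named test, and no place gives an interval method for the difference. The text needs changing on either reading.

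**A reader might infer that the planned test always returns no difference.** The documents do not support that. It would follow only if PPV were restricted to subjects positive on both tests, which the SAP nowhere proposes. The accurate description is that the test is not defined.

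**A reader might infer that the margin is empty at low prevalence in general.** That is too broad. At the assumed 75%/65% the failure appears only at 10%, and for PPV it disappears at 82%/78%. The rule also applies to a lower limit, not a point estimate, which is why a coin flip passes PPV only about 6% of the time.

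**A reader might infer that BDV could win the study while being worse than no test.** The success rule guards against this. Against PCT at 75%/65% (sum 140%), a test whose sensitivity and specificity sum to 100% or less is truly at least 20 points worse on one of them, well beyond the margin. A 65%/55% BDV still beats no test at 10% prevalence (PPV 13.8% against 10%, NPV 93.4% against 90%). This limits the consequence to a misleading secondary statement. It does not make the sentence workable.

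**Conclusion.** The point holds and should be fixed before database lock. On the direct reading, the SAP prescribes for PPV and NPV a test that cannot be run, at the observed prevalence or at any of the four fixed ones. This part needs no distributional assumption.

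The margin is a second, narrower fault. It has no stated basis for predictive values. At 10% prevalence it does not exclude an uninformative test on NPV anywhere in the SAP's PCT range, nor on PPV at the planning values. The simulated pass rates rest on conditional independence and a delta-method limit, and are illustrative.

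PPV and NPV lie outside the co-primary hypotheses, the success rule and the sizing of 97 + 97 events. The harm is confined to the predictive-value comparison in objective 5.

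**What to change.** Replace the sentence in SAP section 6 with:

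> Observed BDV and PCT predictive values are compared with the weighted generalized score test for paired predictive values. For prevalences of 10, 20, 30 and 40%, PPV and NPV are obtained by Bayes' rule from sensitivity and specificity, and the BDV − PCT differences are given with 95% CIs from a subject-level bootstrap stratified by diagnostic truth. These comparisons are secondary, and the -10% margin for sensitivity and specificity is not applied to them.

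This needs a short bootstrap program, no new data and no change in sample size. The price is that no formal non-inferiority claim can be made on PPV or NPV. If the sponsor wants one, it would have to justify a margin for each measure at each prevalence in advance.

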The predicate marker PCT specificity is estimated to be between 56-78% based on a recent review of the published literature (19); PCT specificity will be assumed to be 65% for sample size calculations. BDV specificity is expected to range between 70-80% based on the proof-of-concept study. The study is designed to have at least 80% power and one-sided 2.5% Type I error. A greater than 10% disadvantage for BDV vs PCT (null hypothesis) is to be tested against a less than 10% disadvantage for BDV vs PCT (alternative hypothesis). As shown in Table 2, this non-inferiority hypothesis can also be tested with 97 documented non-infection events. The BDV advantage vs PCT resulting in a -10% one-sided 97.5% lower confidence bound (CB) is also displayed in Table 2; if the specificities are 66.5% for BDV vs 65% for PCT based on 97 pairs of non-infection events, then the one-sided 97.5% lower CB would be -10%, which would establish BDV non-inferiority relative to PCT. A 10% non-inferiority delta with respect to both sensitivity and specificity ensures that the performance of BDV is comparable to PCT, considering the difference in sampling methods and the potentially greater convenience of breath sampling for BDV.

Table 2: One-sided 97.5% Lower Confidence Limit: Specificity Paired Differences simulation)

	Power	N-I
Confidence level, 1-<math>\alpha</math> (one-sided)	0.975	0.975
Expected difference, <math>\pi_T - \pi_S, \Delta_1</math>	0.100	0.015
Proportion discordant, <math>\eta = \pi_{10} + \pi_{01}</math>	0.400	0.315
Proportion both yes, <math>\pi_{11}</math>	0.100	0.100
Lower limit for <math>\pi_T - \pi_S, LL</math>	-0.100	-0.100
Number of simulations	1000	1000
Random seed for simulations	123	123
Power (%)	87	52
n (number of pairs)	97	97

We will also categorize infections per respiratory and non-respiratory infections within our data analysis to determine if there is an impact on the breath delta value.

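### The SAP claims at least 80% study power, but success needs both co-primaries: its own 89% and 87% give about 77% jointly, and about 50% (42% under a less favourable assumption) at the lower end of its expected BDV range.

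*SAP*

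**What the plan says.** SAP section 6 sizes the two co-primary tests separately. Each is a paired non-inferiority comparison of BDV with PCT: "non-inferiority testing will be performed to rule out a -10% disadvantage according to a one-sided 97.5% lower confidence limit".

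- **Sensitivity:** "PCT sensitivity will be assumed to be 75% for sample size calculations" and "BDV sensitivity is expected to range between 80-90% based on the proof-of-concept study". The size claim is that "this non-inferiority hypothesis can be tested with 97 documented infection events". Table 1 gives 89% power for an expected difference of 0.100 and a discordant proportion of 0.400.
- **Specificity:** PCT is assumed to be 65%, and "BDV specificity is expected to range between 70-80% based on the proof-of-concept study". The claim is that "this non-inferiority hypothesis can also be tested with 97 documented non-infection events". Table 2 gives 87% power for the same difference and discordance.

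Both paragraphs contain the sentence "The study is designed to have at least 80% power and one-sided 2.5% Type I error". Earlier in the section, the success rule is "Both endpoints must achieve statistical significance in order to achieve study success". The SAP gives no power for meeting both endpoints and none for a 5-point advantage, the lower end of either expected range.

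**The concern.** The subject of the power sentence is the study, and the study succeeds only if both tests do. The probability of passing two tests is at most that of passing the weaker one, and for independent tests it is the product. Two powers in the high eighties can therefore fall short of 80% together.

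The planning difference of 10 points is also the midpoint of the SAP's own expectation for each endpoint. The reader is not told how quickly power falls toward the lower end of that expectation. The stated 80% is the figure against which a failed study will be read. If it overstates the chance of success, a miss will look like stronger evidence against BDV than it is.

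**Working it through.** **Inputs (all from SAP section 6 unless noted).** n = 97 pairs per endpoint; margin 0.10; one-sided 2.5%, so z = 1.96. The Power columns have difference d = 0.100 and discordance η = 0.400; the N-I columns have d = 0.015 and η = 0.315. SAP section 5 plans equal proportions of infected and uninfected subjects. Its hypotheses place sensitivity in subjects who progress and specificity in those who do not.

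**Formula.** Power of a paired-difference test with a Wald limit: Φ[(d + 0.10) / √((η − d²)/n) − 1.96].

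**Step 1: reproduce the SAP's figures.**
- d = 0.10, η = 0.40: 0.20 / √(0.39/97) = 3.154; 3.154 − 1.96 = 1.194; power 88.4%. The tables give 89% and 87%.
- d = 0.015, η = 0.315: power 52.3%. The tables give 51% and 52%.

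Enumerating the exact trinomial probabilities for the planning case gives 88.2% with a Wald limit and 88.1% with the Tango score test. The per-endpoint figures are sound.

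**Step 2: joint power in the planning case.** From the SAP's figures, 0.89 × 0.87 = 77.4%. From the formula, 0.884² = 78.1%. Without independence, the joint power lies between 0.89 + 0.87 − 1 = 76% and min(0.89, 0.87) = 87%.

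**Step 3: discordance at a 5-point advantage.** The SAP does not state it. In both tables the share that only PCT classifies correctly is (η − d)/2: (0.400 − 0.100)/2 = 0.15 and (0.315 − 0.015)/2 = 0.15. Holding that share fixed gives η = 0.30 + d, so η = 0.35 at d = 0.05. For sensitivity this agrees with the rest of Table 1: both-yes is 0.60, PCT is 0.60 + 0.15 = 0.75, BDV is 0.60 + 0.20 = 0.80, and discordance is 0.15 + 0.20 = 0.35.

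**Step 4: power across the expected range** (both endpoints at the same advantage).

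| Case | d | η | Per endpoint | Both |
|---|---|---|---|---|
| Planning | 0.10 | 0.40 | 88.4% | 78.1% |
| Lower end, tables' pattern | 0.05 | 0.35 | 70.8% | 50.1% |
| Lower end, discordance held | 0.05 | 0.40 | 64.9% | 42.1% |
| Upper end, tables' pattern | 0.15 | 0.45 | 96% | 93% |

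For the second row: 0.15 / √(0.3475/97) = 2.506; 2.506 − 1.96 = 0.546; Φ = 70.8%. If only sensitivity is at its lower end (η = 0.35) and specificity is as planned, joint power is 0.708 × 0.884 = 62.5%.

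**Step 5: size of the planning gap.** About 101 pairs per endpoint would give 89.6% each and 0.896² = 80% jointly, 4 pairs more than planned in each group.

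**Step 6: form of the test.** Section 6 also names exact McNemar tests. As a rough indication of what a more conservative test does, a continuity-corrected Wald limit gives 85.1% per endpoint and 72% jointly in the planning case. At the lower end it gives 42% jointly (η = 0.35) or 36% (η = 0.40).

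**The case against.** The strongest defence is that the power sentence stands once in each endpoint's paragraph and can be read as a claim about that endpoint. On that reading 89% and 87% both satisfy it, and the defect is an omitted joint figure rather than a false one. That is a fair reading of the layout. It does not remove the point, because the sentence speaks of the study, success requires both tests, and no joint power is given.

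Other objections hold in part.

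- **The planning gap is small.** It is 2 to 3 points. With 1000 simulations per table, the 77.4% product itself has a Monte Carlo 95% interval of about 74.9% to 79.9%.
- **Planning at the midpoint is ordinary practice.** The SAP nowhere claims 80% power across the whole expected range, and at the upper end joint power is about 93%. The lower-end figures are information that the reader needs, not an arithmetic error by the SAP.
- **Independence is an assumption.** Section 6 counts infection and non-infection events and records onset and resolution dates. If one subject can supply both kinds, the product is not exact, and only the 76% to 87% bounds hold.

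A reader might infer that 42% is the SAP's own joint power at the lower end. The documents do not support that as the headline. It requires discordance to stay at 0.40 while the difference halves. For sensitivity that contradicts Table 1: with PCT at 75% and BDV at 80%, discordance of 0.40 needs both-yes of 0.575, not 0.60. For specificity the SAP is less clear. If Table 2's both-yes of 0.10 means both tests falsely positive and is held fixed, discordance at 70% against 65% is 0.45 and power about 60%, which with 71% for sensitivity is again about 42% jointly. Table 2's N-I column does not follow that rule, however. So 42% belongs in the text as the less favourable assumption, beside 50%.

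**Conclusion.** The stated power is not the probability of meeting the SAP's success rule. On the SAP's own figures that probability is about 77%, a shortfall of about 3 points. At the lower end of the expected BDV range it is about 50% with discordance 0.35, or 42% with discordance 0.40, and neither endpoint alone reaches 80% under either value.

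These figures rest on three conditions: independence of the two tests, 97 pairs actually obtained for each endpoint, and a simple confidence-limit method that reproduces the tables. The second condition is not assured: Protocol section 7.1 plans 100 subjects with 5 infected, whereas the SAP assumes equal infected and uninfected groups.

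It would be too much to conclude that the tables are wrong or that Type I error is affected. The per-endpoint powers reproduce, and requiring both endpoints does not inflate the error rate. Power at equal accuracy should not be brought in either, since it lies outside the range that the SAP expects.

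**What to change.** In SAP section 6, replace the power sentence in both paragraphs with one statement:

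> With 97 pairs per endpoint, a 10-point BDV advantage and discordance 0.40, power is 89% for sensitivity and 87% for specificity, and about 77% to meet both, assuming independence; with a 5-point advantage on each, joint power is about 50% at discordance 0.35 (42% at 0.40).

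Add that these figures are conditional on obtaining 97 + 97 pairs and on the confidence-limit method used in the simulations. Then recompute them under the exact test that the section names, and print those values if they differ.

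The sample size, margin, tests and success rule do not change. The cost is a revised paragraph, one further power run, and a stated figure that is less favourable than the present one.
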